#### **4.9.3. Anti-Drug Antibodies**

Individual anti-drug antibody (ADA) data will be listed.

The frequency and percentage of ADA responses will be summarized by treatment group and scheduled time.

The frequency and percentage of all patients testing positive for ADA at any point during the study (i.e. ADA prevalence) will be summarized by treatment group. This will include summaries of the prevalence ADA confirmed as “Anti-ACE-083” or “Anti-FST315”. In addition, for ACE-083 ADA, a summary of the prevalence of ACE-083 ADA and titer summary (median, minimum, and maximum value) will be provided by scheduled visit and antibody follow-up visit (as applicable).

The ACE-083 ADA incidence is defined as the sum of both “treatment-induced” and “treatment-boosted” ACE-083 ADA positive subjects as a proportion of patients with at least one sample taken post study drug administration that is appropriate for ADA testing. Treatment induced ACE-083 ADA is defined as ACE-083 ADA developing de novo following study drug administration at any time following the first study drug administration in a patient without pre-existing ACE-083 ADA. Treatment boosted ACE-083 ADA is defined as a pre-existing ACE-083 ADA that was boosted to a higher level following study drug administration. ACE-083 ADA incidence will be summarized by treatment group.

Additional analyses may be performed as appropriate.

#### **4.9.4. Other Safety Data**

Not applicable.

### **4.10. Pharmacokinetic Data**

Pharmacokinetic data will be summarized under the direction of the Acceleron Clinical Pharmacologist and summaries will be outlined in a separate analysis plan.

## 5. MODIFICATIONS FROM THE STATISTICAL SECTION OF THE PROTOCOL

The following modifications from the statistical section of the protocol have been implemented in the statistical analysis plan:

- For statistical analyses where confidence intervals for the least-squares mean are provided, the 95% confidence interval will be provided in addition to the 90% confidence interval.
- The “Safety Population” is now called the “Safety Set”.
- For muscle strength, “Peak force value” is now called “MVIC”.
- For motor function data (lower leg and upper arm functional assessments), strength (QMT by handheld device), gait, and FSHD-HI data whose pre-treatment assessments are performed up to three times prior to the first dose, the baseline is defined as the average of the non-missing values.
- The “Per Protocol Set” is defined as all patients enrolled/randomized in the study who have received at least one dose of study drug (includes placebo) with no major protocol violations.
- The last observation carried forward approach is not being performed in the statistical analyses. Standard multiple imputation will be performed to assess the impact of missing data on the observed data.

## 6. PROGRAMMING SPECIFICATIONS

### Seed to Use for Multiple Imputations of Missing Data

The seed to be used for multiple imputations of MRI data is 1111.

The seed to be used for multiple imputations of FSHD-HI data is 2222.

The seed to be used for multiple imputations of TA functional data is 3333.

The seed to be used for multiple imputations of PUL data is 4444.

The seed to be used for multiple imputations of elbow flexion MVIC data is 5555.

The seed to be used for multiple imputations of ankle dorsiflexion MVIC data is 6666.

### Representation of Scheduled Times in Listings

Because data for this study comes from multiple sources, such information will be standardized in the listings. The standardization is outlined below:

Lab (MRL), FSHD-HI, eCRF (long)	eCRF (short)	MRI	Mapping for Tables and Listings	Plots
Screening Day -28	SCN		S1D-28	-28
Screening Day -7	SCN2		S2D-7	-7
Cycle 1 Day 1	C1D1	DAY 1	C1D1	1
Cycle 1 Day 2	C1D2		C1D2	2
Cycle 1 Day 8	C1D8		C1D8	8
Cycle 2 Day 22	C2D22		C2D22	22
Cycle 3 Day 43	C3D43	DAY 43	C3D43	43
Cycle 4 Day 64	C4D64		C4D64	64
Cycle 5 Day 85	C5D85		C5D85	85
Cycle 5 Day 86	C5D86		C5D86	86
Follow-Up Day 106/ET a	ET	DAY 106	F1D106_ET	106
Cycle 6 Day 106 b	C6D106	DAY 106	C6D106	106
Cycle 7 Day 127 b	C7D127		C7D127	127
Follow-Up Day 141 a	FUP	DAY 141	F2D141	141
Cycle 8 Day 148 b	C8D148		C8D148	148

Lab (MRL), FSHD-HI, eCRF (long)	eCRF (short)	MRI	Mapping for Tables and Listings	Plots
Cycle 9 Day 169 b	C9D169		C9D169	169
Cycle 10 Day 190 b	C10D190	DAY 190	C10D190	190
Cycle 11 Day 211 b	C11D211		C11D211	211
Cycle 12 Day 232 b	C12D232		C12D232	232
Cycle 13 Day 253 b	C13D253		C13D253	253
Cycle 14 Day 274 b	C14D274		C14D274	274
Cycle 15 Day 295 b	C15D295	DAY 295	C15D295	295
Cycle 16 Day 316 b	C16D316		C16D316	316
Cycle 17 Day 337 b	C17D337		C17D337	337
Day 358/ET b	ET	DAY 358	F1D358_ET	358
Follow-Up Day 393 b	FUP	DAY 393	F2D393	393

a Applies to Part 1; b Applies to Part 2

### Partial Date of Birth Entries

In the event that a patient does not have a complete date of birth present in the clinical database, the date of birth will be interpolated as follows:

- If the date of birth contains the month and year of birth but no value of day (i.e. day is missing or has value “UNK”), the value of day will be imputed to the 1st for purposes of any calculations that involve the complete birthdate of the patient (i.e. age).
- If the date of birth only contains the year but no value of month and day (i.e. “UNK-UNK-yyyy”), the birthdate will be imputed to “01-Jan-yyyy” where “yyyy” refers to the year that is reported for that patient for purposes of any calculations that involve the complete birthdate of the patient (i.e. age).

### Partial AE Start Dates

The following rules will be utilized for partial AE start dates:

- If the year is unknown, the date will not be imputed and will be assigned a missing value.
- If the month is unknown, then:
  - If the year matches the first dose date for the patient with the partial AE start date, then the month and day of the first dose date will be imputed.

- Otherwise, the month will be imputed to January.
- If the day is unknown, then:
  - If the month and year match the first dose date, then the day of the first dose date will be imputed.
  - Otherwise, the day will be imputed to '01'.

### Classification of Aes as Teaes

In general, the start of reporting of adverse events for an individual patient starts after receiving the first dose of study drug. However:

- If both the AE start and stop date exist and are before the first dose date of study drug, the AE will be classified as a pre-treatment AE and not considered treatment emergent.
- If the AE start date is on or after the first dose date of study drug, the AE will be considered a TEAE.
- If the AE start date is before the first dose date of study drug and the AE stop date is after the first dose of study drug and the AE worsened in intensity, the AE will be considered a TEAE.
- If the AE start date is missing and the stop date is before the first dose of study drug, the AE will be not be considered a TEAE.
- If the AE start date is missing and the stop date is after the first dose of study drug, the AE will be considered a TEAE.
- If the AE start and stop dates are missing, the AE will be considered a TEAE.

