## 4.5. Prior and Concomitant Medications/Therapy

Prior and concomitant medications recorded during the study will be listed. These will be coded with the WHO Drug Dictionary (Version 2016-09).

Medications will be assigned as prior or concomitant based on the following rules:

- If both the start and stop date exist and are before the first dose date of study drug, the medication will be classified as a prior medication.
- If the start date is on or after the first dose date of study drug, the medication will be classified as a concomitant medication.
- If the start date is before the first dose date of study drug and the stop date is after the first dose date of study drug or the medication is ongoing, the medication will be classified as prior and concomitant.
- If the start date is missing and the stop date is before the first dose of study drug, the medication will be classified as prior.
- If the start date is missing and the stop date is after the first dose of study drug or the medication is ongoing, the medication will be classified as concomitant.
- If the start and stop dates are missing, the medication will be classified as concomitant.

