## **4.9. Safety Data**

### **4.9.1. Adverse Events**

Adverse events (AEs) will be coded using MedDRA Version 19.1.

All AEs will be listed and will include but not necessarily be limited to the following: verbatim term, MedDRA preferred term, treatment group, severity, relationship to study medication,

action taken with respect to study medication, and whether or not the AE is treatment-emergent although not necessarily in that order.

Treatment-emergent AEs (TEAEs) are defined those AEs that start or worsen in intensity on or after the first study drug administration up to the end of the follow-up period (Day 141 [Part 1] / Day 393 [Part 2]). AEs classified as TEAEs will be summarized. Planned summaries include the following (for each muscle group unless otherwise specified):

- Overall summary of TEAEs by treatment group
- Summary of TEAEs by MedDRA System Organ Class and Preferred Term for each treatment group – Number of Patients
- Summary of TEAEs by MedDRA System Organ Class and Preferred Term for each treatment group – Number of Events
- Summary of TEAEs by MedDRA Preferred Term for each treatment group – Number of Patients
- Summary of TEAEs by MedDRA Preferred Term for each treatment group – Number of Events
- Summary of CTCAE Grade 3 or Higher TEAEs by MedDRA System Organ Class and Preferred Term for each treatment group – Number of Patients
- Summary of CTCAE Grade 3 or Higher TEAEs by MedDRA System Organ Class and Preferred Term for each treatment group – Number of Events
- Summary of CTCAE Grade 3 or Higher TEAEs by MedDRA Preferred Term for each treatment group – Number of Patients
- Summary of CTCAE Grade 3 or Higher TEAEs by MedDRA Preferred Term for each treatment group – Number of Events
- Summary of TEAEs possibly or probably related to study drug by MedDRA System Organ Class and Preferred Term for each treatment group – Number of Patients
- Summary of TEAEs possibly or probably related to study drug by MedDRA System Organ Class and Preferred Term for each treatment group – Number of Events
- Summary of TEAEs possibly or probably related to study drug by MedDRA Preferred Term for each treatment group – Number of Patients
- Summary of TEAEs possibly or probably related to study drug by MedDRA Preferred Term for each treatment group – Number of Events
- Summary of TEAEs by MedDRA Preferred Term by CTCAE Grade and Relationship to Drug for each treatment group – Number of Patients

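### The SAP's date rules for treatment-emergent events give no rule for a pre-dose event that worsened and is still ongoing, and can count an event that ended before treatment

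*SAP*

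**What the plan says.** SAP section 4.9.1 gives the governing definition: "Treatment-emergent AEs (TEAEs) are defined those AEs that start or worsen in intensity on or after the first study drug administration", with follow-up to Day 141 in Part 1 and Day 393 in Part 2. It sets no condition on resolution. It then says "AEs classified as TEAEs will be summarized", so the flag decides what enters the tables.

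SAP section 6, under the heading on classifying AEs as TEAEs, makes the definition operational in six bullets. The third is the only one for an event with onset before the first dose that later worsened. It opens "If the AE start date is before the first dose date of study drug and the AE stop date is after the first dose", and worsening is its further condition. The last bullet deals with a missing stop date, but only when the start is missing too: "If the AE start and stop dates are missing, the AE will be considered a TEAE".

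The parallel rule for medications in SAP section 4.5 has the branch that the AE rule lacks: "the stop date is after the first dose date of study drug or the medication is ongoing".

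For incomplete AE start dates, section 6 says that if the month is unknown and the year is that of the first dose, "then the month and day of the first dose date will be imputed". A start with only the day unknown, in the month and year of the first dose, is handled the same way. Neither rule refers to the stop date.

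**The concern.** Safety is the primary objective of Part 1 and a secondary objective of Part 2, and the TEAE tables are its main summary. The operational rules should reproduce the definition in 4.9.1, and in two places they do not.

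- The worsened-event rule recognises a worsening only once the event has a stop date. Protocol section 13.5 follows AEs until database lock, or until resolution if that comes sooner, so an event can reach lock without one. The case left without a rule is the less favourable one: the worsening that did not resolve.
- The partial-date rule can move the start of an event past its own known end, which brings an event that was over before treatment into the TEAE count.

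Both leave the result to the programmer's reading, in a document whose stated purpose is to fix the analysis before lock.

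**Working it through.** The plan states no figure on this point, so the check is a decision table. I applied the six bullets, numbered 1 to 6 in SAP order, to the combinations of start date, stop date and worsening, and compared the result with 4.9.1, under which an event counts if it should "start or worsen in intensity on or after the first study drug administration up to the end of the follow-up period".

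| Start | Stop | Worsened on drug | Section 6 | Section 4.9.1 |
|---|---|---|---|---|
| Before first dose | After first dose | Yes | TEAE (bullet 3) | TEAE |
| Before first dose | None (ongoing) | Yes | No rule | TEAE |
| Before first dose | On first-dose date | Yes | No rule | TEAE |
| Before first dose | After, or none | No | No rule | Not a TEAE |
| On or after first dose | Any, or none | Either | TEAE (bullet 2) | TEAE |
| Missing | Before first dose | Either | Not a TEAE (bullet 4) | Not a TEAE |
| Missing | On first-dose date | Either | No rule | Not decidable from dates |
| Missing | After first dose | Either | TEAE (bullet 5) | Not decidable from dates |
| Missing | Missing | Either | TEAE (bullet 6) | Not decidable from dates |

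The second row is the main gap. The third row and the missing-start, first-dose-date row are boundary gaps: bullets 3 and 5 ask for a stop strictly after the first dose, and the two explicit exclusions (bullets 1 and 4) ask for a stop strictly before it. Bullet 3 also does not say when the worsening happened, whereas 4.9.1 places it on or after the first dose.

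Partial start, with illustrative dates: first dose 20 February 2018, stop 5 February 2018, start known only as 2018.

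1. The year matches the first dose, so the start is imputed as 20 February 2018, 15 days after the stop (20 − 5).
2. Bullet 1 needs start and stop both before the first dose. The imputed start is not, so bullet 1 fails.
3. Bullet 2 needs a start on or after the first dose. It is met, so the event is a TEAE.
4. With the start missing altogether, bullet 4 makes the same event not a TEAE. The less complete date gives the right answer.

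A start known only as February 2018 is imputed to the same date and misclassified in the same way.

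How many tables one record touches: section 4.9.1 lists 1 overall summary, 4 of all TEAEs, 4 of Grade 3 or higher, 4 of possibly or probably related events, and 2 by grade and relationship, so 1 + 4 + 4 + 4 + 2 = 15 TEAE summaries, plus one of serious events.

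- Unrelated, Grade 1–2: 1 + 4 + 2 = 7 tables.
- Related Grade 1–2, or unrelated Grade 3 or higher: 7 + 4 = 11.
- Related and Grade 3 or higher: 15.

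Weight of one patient in a row of a table: 1/14 = 7.1 percentage points in a planned Part 2 arm for one muscle, and 1/6 = 16.7 points in a Part 1 cohort.

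**The case against.** A reader might infer that an unresolved worsening is excluded from every TEAE table. The documents do not support that. Section 6 is silent on the ongoing case; its only explicit exclusions need a stop date before the first dose, and 4.9.1 includes the event. A programmer who follows 4.9.1 will flag it, and one who codes only the listed conditions will not. Nor does every event belong in all 15 summaries: an unrelated Grade 1–2 event belongs in 7.

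The strongest counter-argument is that such records should be rare. Protocol section 13.1.1 defines an AE as occurring on or after the first dose. Section 13.4 sends anything between consent and first dose to the medical history form. Section 13.1.1.2 removes a pre-existing condition from the AE definition only if it does not worsen. A condition that worsens and is entered with the date of worsening as its onset is caught by bullet 2, resolved or not. The partial-date fault needs a pre-dose event on the AE form, an incomplete start and a known earlier stop together. It errs toward over-counting, and a start later than its stop is a discrepancy that the data review in protocol section 16.1 could catch. All AEs are listed with their treatment-emergent status, so nothing disappears from view.

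This argument stands as a limit on frequency. It does not make the rules right. Section 6 itself expects exceptions, since it supplies rules for events starting before the first dose, and the documents do not say which onset date a site enters when a pre-existing condition worsens.

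A further inference, that the comparison between arms is biased, is also unsupported. The rules apply alike to active drug and placebo, and nothing in the documents shows a difference.

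**Conclusion.** The point holds and is minor. The six rules leave a worsened, ongoing event with pre-dose onset unclassified, contrary to 4.9.1, and the partial-start rule can classify an event that ended before treatment as a TEAE.

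The number of affected records cannot be derived from the documents and is probably small. The 7.1 and 16.7 points are the weight of one patient in one row, such as a preferred term; the overall TEAE percentage does not move if that patient has any other TEAE. The conclusion assumes that an ongoing event carries no stop date, and that some AE records keep an onset before the first dose, which the recording rules make the exception.

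**What to change.** In SAP section 6:

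1. Third bullet: require that the start is before the first dose, that the worsening occurred on or after the first dose, and that the AE stop date is on or after the first-dose date or the AE is ongoing. This matches 4.9.1 and the form already used for medications in 4.5.
2. Fifth bullet: change a stop after the first dose to a stop on or after it.
3. Partial AE start dates: do not impute the start to the first-dose date when the known stop date is before the first dose; classify that event as pre-treatment.

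The cost is two or three lines of SAP text and the matching program lines. No new data are needed.

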### Unilateral vs. Bilateral (Part 1)

In Part 1 of this study, patients may be treated unilaterally (meaning that the patient receives his/her dose either on the left TA or BB muscle or the right TA or BB muscle) or bilaterally (meaning that the patient receives his/her dose on both the right and left sides).

For patients receiving ACE-083 unilaterally, the side treated will vary from patient to patient within a cohort. To properly identify the side treated, the dataset(s) that identify the dose administrations for the individual patient will be used.

### Patients that Discontinue Early

For patients that discontinue early, end-of-treatment and follow-up assessments will be completed and analyzed as such.

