Strength (QMT – by handheld device) ¹²	X	X	X	X	X	X	X	X	X	X	X	X	X	X	X	X	X		
Lower Leg Functional Assessments ¹³	TA & BB	TA & BB	TA		TA	TA	TA	TA	TA	TA	TA	TA	TA	TA & BB Day 190		TA	TA	TA & BB	
Upper Arm Functional Assessments ¹⁴	BB & TA	BB & TA	BB		BB	BB	BB	BB	BB	BB	BB	BB	BB	BB & TA Day 190		BB	BB	BB & TA	
FSHD-Health Index	X	X	X		X	X	X	X	X	X	X	X	X	X		X	X	X	
Monitoring of concomitant medications	X	X	X	X	X	X	X	X	X	X	X	X	X	X	X	X	X	X	
Monitoring of adverse events			X	X	X	X	X	X	X	X	X	X	X	X	X	X	X	X	
Randomization ¹⁵			X																
Study drug administration ¹⁶			X			X	X	X	X	X	X	X	X	X	X	X			
MMT assessment (MRC)	X													X			X	X	

¹ Study procedures must be done prior to administration of study drug. Reference the Study Manual for the order of study procedures. Laboratory samples and functional/strength assessments may be collected up to 24 hours prior to administration of study drug. Time of study drug administration is the time of the first injection. The Day 1 visit is timed relative to the Screening Day -28 to Day -21 visit. The Day -7 visit is timed relative to the scheduled Day 1 visit.

² All visit day windows should be considered relative to the date of the previous dose of study drug. Actual visit days may be different than planned (e.g., Day 8, Day 22) due to windows on visits and potential dosing delays.

³ Pregnancy test for women of childbearing potential to be performed and negative result confirmed before dosing.

⁴ Genetic testing for FSHD1/FSHD2 to be performed at screening if patient has not already had testing performed or previous results cannot be used to determine eligibility. Genetic testing for FSHD1/FSHD2 to be performed during the study if first degree relative is used for study eligibility but patient has not had testing previously performed or if patient's genetic documentation is inadequate with respect to FSHD1 D4Z4 fragment size or repeat number

⁵ Full physical examination includes skin, head, eyes, ears, nose, throat and neck, lymph nodes, cardiovascular, respiratory, gastrointestinal, musculoskeletal, and neurological

⁶ Limited physical examination includes skin, cardiovascular, respiratory, musculoskeletal and neurological assessments

⁷ Injection site examination including but not limited to evaluating erythema, pain, bruising, bleeding, and other signs of discomfort or skin reaction to be completed at least 30 minutes after injection.

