⁸ Vital signs (weight, heart rate, systolic and diastolic blood pressure) must be taken prior to administration of study drug on dosing days. Height is collected only at screening.

⁹ Tests defined in [Appendix 2, Table 7](#).

¹⁰ PK samples on a dosing day have a \pm 15 minute window for post-dose sample collection, based on the time of the first injection. Pre-dose samples may be collected up to 4 hours prior to dosing. Day 2 and 86 sample collection should be 24 hours post dose \pm 3 hours.

¹¹ MRI assessments should be completed within 5 days prior of the scheduled dose administration. MRI assessments during the follow up period (Day 358/ET and Day 393/EOS) have a \pm 5 day window

¹² Maximum voluntary isometric contraction testing (MVICT) of both TA and BB muscles will be conducted for all cohorts at screening visits, Day 190 and Day 393/EOS. At all other visits, only the muscle under study will be tested (i.e., TA or BB). Both sides will be tested for all visits (right and left).

¹³ TA cohort only: 10-meter walk/run, 4-stair climb, 6-minute walk test, and gait analysis are performed at all visits: 100-meter timed test begins at Day 169 and continues throughout open-label visits; lower leg assessments will be collected for the BB cohorts at screening visits, Day 190 and Day 393/EOS only.

¹⁴ BB cohort only: PUL mid-level/elbow dimension performed at all visits; additional PUL high level/shoulder dimension begins at Day 169 and continues throughout open-label visits; PUL testing will also be performed on patients in TA cohorts at screening visits (mid level), Day 190 (high and mid-level) and Day 393/EOS (high and mid-level) only.

Non-ambulatory patients in the BB cohort can opt out of the TA assessments.

¹⁵ Randomization should occur within 24 hours prior to Day 1 dose.

¹⁶ Study drug administration should occur within 21 days (\pm 3 days) of the last dose.

¹⁷ Patients who discontinue prior to the Day 358/ET visit should complete the Day 358/ET visit at the time of discontinuation and return for the remaining follow-up period visit. If an MRI has been completed within 4 weeks of discontinuation, it does not need to be repeated as part of the Day 358/ET visit procedures.

¹⁸ If a patient has a positive ADA result at Day 393/EOS, the patient will be asked to return to the clinical site for additional follow-up approximately every 3 months until a negative or stable result is obtained.

¹⁹ ECG is to be conducted \pm 1 hour of the 4h PK sample.

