## 4.2. Analysis Population

The analysis populations include the following:

- Full Analysis Set: Part 1 – All patients enrolled in the study receiving at least one dose of ACE-083. Part 2 – All patients randomized;
- Safety Set: All patients enrolled/randomized in the study who have received at least one dose of study drug (includes placebo);
- Per Protocol Set: All patients enrolled/randomized in the study who have received at least one dose of study drug (includes placebo) with no major protocol violations.
  - Major protocol violations include:

- Patients who discontinue the study prior to the Cycle 3 Day 43 visit; these patients are replaced per protocol
- Patients whose Day 1 MRI or Day 190 MRI was done 7 or more days following study drug administration
- Patients whose functional assessments (i.e. 10mW/R, mid-level PUL, 6MWT, 4-stair climb) at Day 1 or Day 190 were done 7 or more days following study drug administration
- Patients who did not receive the full study drug administration planned per protocol at all injection sites on any or both sides (right or left) for 2 or more consecutive visits for reasons other than dose reductions for the safety of the patient or feasibility concern (i.e., the site intended to administer the full dose but was unable).

Should the statistical analysis populations be identical (e.g., Full Analysis Set = Per Protocol Set), statistical analyses will not be duplicated or repeated.

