#### **4.3. Subject Disposition**

Individual patient disposition data will be listed.

Frequency counts will be tabulated for disposition data and will include the following:

- Number of patients enrolled [Part 1 only],
- Number of patients randomized [Part 2 only],
- Number (%) of patients completing the study [Part 1 only],
- Number (%) of patients completing the double-blind treatment period [Part 2 only]
  - A patient is said to have completed the double-blind treatment period if the patient completed up to and including the Day 190 visit.
- Number (%) of patients entered into the open-label period [Part 2 only]
- Number (%) of patients completing the open-label treatment period [Part 2 only]
  - A patient is said to have completed the open-label treatment period if the patient completed up to and including the Day 337 visit.
- Number (%) of patients that rollover to the extension study, A083-04
  - Patients that rollover to the extension study consist only of patients participating in Part 2 of this study who complete both the double-blind treatment period AND the open-label treatment period who will not have the Day 393/EOS visit. These patients' final study visit will be the Day 358/ET visit.
- Number (%) of patients that do not rollover to the extension study A083-04
  - Patients that do not rollover to the extension study will have both the Day 358/ET and Day 393/EOS visits completed.

- Number (%) of patients discontinuing from the study prior to completing both the double-blind period and the open label period [Part 2 only]
  - Number (%) of patients that discontinued during the double-blind period
  - Number (%) of patients that discontinued during the open-label period
  - Number (%) of patients for primary reason for discontinuation will also be provided [provided there is at least one patient who discontinued].

Summaries will be provided by treatment and overall for each study part (Part 1 and Part 2).

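### Part 2 early-termination values share the Day 358 label with no rule to separate them, so as written they count as observed Day 358 data and are not imputed

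*SAP*

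**What the plan says.** **Timing of the visit.** Protocol Appendix 1, Table 6, footnote 17: "Patients who discontinue prior to the Day 358/ET visit should complete the Day 358/ET visit at the time of discontinuation". The actual day can therefore be any day on which a patient stops. The same footnote waives the scan in some cases: "If an MRI has been completed within 4 weeks of discontinuation, it does not need to be repeated".

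**Label.** The visit map in SAP Section 6 (Representation of Scheduled Times in Listings) has one Part 2 row for Day 358 and ET. Its MRI label is DAY 358, its table and listing label is F1D358_ET, and its plot position is 358.

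**Handling of leavers.** SAP Section 6 (Patients that Discontinue Early): "For patients that discontinue early, end-of-treatment and follow-up assessments will be completed and analyzed as such".

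**Use of Day 358.** SAP 4.7.2.3 summarises open-label data by scheduled time. It also compares the change from open-label baseline to Day 358 with the change over the first six months, with tests at the two-sided 0.10 level. Multiple imputation is applied where data are missing, and the imputed analysis is primary.

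**Carrying forward.** SAP Section 5: "The last observation carried forward approach is not being performed in the statistical analyses".

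**The concern.** The label says Day 358 but the measurement may have been taken months earlier. Read together, these provisions put an early leaver's ET value into the Day 358 slot. Because the slot is filled, the value is not missing and the imputation never reaches it. For such a patient the last observation stands in for Day 358, which is what the SAP says it no longer does.

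What is at stake is the meaning of the open-label results. Day 358 means, plots and the first-versus-second six-month comparisons could mix full eight-dose courses with much shorter ones, in sequence groups of at most 14. The label also falls on patients who leave in the double-blind period, because their ET visit is the same Day 358/ET visit. Their values can enter the raw Day 358 summaries and plots.

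**Working it through.** The plan gives no figure on this point, so the first step is to look for any rule that would separate the two kinds of value.

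**1. Search for a separating rule**

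- SAP 4.1.5 limits descriptive statistics to protocol-planned visits. Day 358/ET is a planned visit, so the rule admits it.
- SAP 4.1.5 has a 7-day timing rule for late Day 190 assessments. There is no counterpart for Day 358.
- The protocol's visit windows govern scheduling: "All visit day windows should be considered relative to the date of the previous dose of study drug". Nothing uses them to select values for analysis.
- The Per Protocol exclusion for discontinuation (SAP 4.2) reaches only patients who leave before Day 43.
- The ET label does not itself identify leavers. Under SAP 4.3, completers who roll over to the extension study also finish at Day 358/ET.

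No rule was found.

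**2. MRI and the 4-week waiver**

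On-treatment scans have a lead time: "MRI assessments should be completed within 5 days prior of the scheduled dose administration". The open-label period has scheduled scans at Day 190 and Day 295.

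| Scan | Possible scan days | Last waived day (scan day + 28) | First unwaived day |
|---|---|---|---|
| Day 190 | 185 to 190 | 213 to 218 | 214 to 219 |
| Day 295 | 290 to 295 | 318 to 323 | 319 to 324 |

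A leaver at Day 212 is 22 to 27 days from the Day 190 scan and needs no ET scan. With none done, Day 358 is missing and is imputed. A leaver at Day 219 is 29 to 34 days away and has a scan labelled Day 358. Around the second scan, a leaver at Day 316 (21 to 26 days) is waived and one at Day 324 (29 to 34 days) is not. Near-identical leavers are thus handled in opposite ways.

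**3. Illustration of size**

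Assumptions, not taken from the documents for this comparison: a linear gain of 10 points from Day 190 to Day 358, and all 14 patients of a sequence group analysed.

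- Interval: 358 − 190 = 168 days.
- Shortfall of a value taken on day d: 10 × (358 − d)/168.
- Dilution of the group mean with k leavers: k × shortfall/14.

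| Case | Shortfall | Dilution (points) |
|---|---|---|
| Non-MRI, one leaver, Day 295 | 10 × 63/168 = 3.75 | 3.75/14 = 0.27 |
| Non-MRI, two leavers, Day 211 | 10 × 147/168 = 8.75 | 2 × 8.75/14 = 1.25 |
| MRI, two leavers, Day 219 | 10 × 139/168 = 8.27 | 2 × 8.27/14 = 1.18 |
| MRI, two leavers, Day 214 | 10 × 144/168 = 8.57 | 2 × 8.57/14 = 1.22 |
| MRI, two leavers, Day 324 | 10 × 34/168 = 2.02 | 2 × 2.02/14 = 0.29 |
| MRI, two leavers, Day 319 | 10 × 39/168 = 2.32 | 2 × 2.32/14 = 0.33 |

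If the gain after Day 190 is zero, every shortfall is zero.

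**The case against.** **The wording may be deliberate.** The sentence on early leavers can be read as an instruction to analyse those visits as end-of-treatment visits. That reading is fair as to intent. It does not help in practice, because the SAP defines no ET summary, model or plot position other than Day 358.

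**The remedy may be a preference.** A value at discontinuation and a Day 358 value imputed under missing at random answer different questions, and neither is wrong in itself. That stands as a general point. Here, however, the SAP has made imputation its primary approach and set carrying forward aside, so the visit map works against the plan's own choice.

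**The illustration is not evidence.** The 10% in the sample size section is an active-versus-placebo difference for the double-blind period. Nothing supports a further linear gain of that size, least of all in patients already treated for six months. This stands in full.

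**Stronger readings a reader might infer:**

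- *That the Day 190 primary analysis is contaminated.* The documents do not show this. The shared label is Day 358, not Day 190.
- *That the Per Protocol Set removes leavers who miss two or more doses,* through the bullet on administrations not fully given "for 2 or more consecutive visits for reasons other than dose reductions for the safety of the patient or feasibility concern". That bullet describes visits at which a full dose was intended but could not be given, and discontinuation has its own bullet. It is not a sound basis for a separate Per Protocol estimate, and none is given here.
- *That the SAP formally performs last observation carried forward.* It does not. The effect is the same only for leavers who have an ET value.

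**Conclusion.** The plan is wrong as written, and the point is minor. Followed literally, the visit map places early ET values in the Day 358 slot, no rule takes them out, and the imputation does not touch them. The consequences fall on the open-label summaries, plots and second-six-month comparisons. For double-blind leavers, the point goes no further than raw Day 358 summaries and plots.

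The size cannot be determined, because the documents give no open-label drop-out rate and no open-label time course. Under the stated illustration, dilution is 0.27 to 1.25 points for non-MRI measures. For MRI with two leavers it is 1.18 to 1.22 just after the Day 190 waiver ends and 0.29 to 0.33 just after the Day 295 waiver ends. It is near zero where there is no further gain, as may be so in the ACE-083 to ACE-083 sequence.

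**What to change.** In SAP Section 6:

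1. Give early termination its own label, distinct from Day 358.
2. Count an assessment as Day 358 only if the patient completed the open-label treatment period and did not discontinue before the scheduled Day 358 visit. SAP 4.3 already defines completion: "A patient is said to have completed the open-label treatment period if the patient completed up to and including the Day 337 visit". Set no strict day limit, so that completers with dosing delays or slightly out-of-window visits keep their real values.
3. Otherwise list and summarise the value as ET with its actual study day, and do not plot it at 358. Treat Day 358 as missing and, in the second-six-month comparisons, impute it under the rules already in SAP 4.7.2.3.
4. Report the version that uses ET as Day 358 as a sensitivity analysis.

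The cost is a few lines of text and a derivation from visit and dose dates already collected. The downside is slightly more programming and a few more imputed values in small groups. The observed ET values are still used in the sensitivity analysis.
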